The total number of participants that will be enrolled into the 6-month feasibility trial is 70. It is estimated that we will screen ~1,700 participants to achieve this recruitment goal. Since the initial contact is via an online link, there will be many incomplete responses driving up the number of screened-out participants.

How was sample size determined?

We based the sample size of 70 for this pilot feasibility trial on necessities for examining feasibility. This sample size allows us to recruit online groups of 35 which we have demonstrated in an ongoing study is feasible and breeds regular engagement. Our previous work with smaller online groups (i.e., n=12)^{33,34} showed that presence of a few quiet participants can result in a fairly rapid decline engagement among entire group.^{33,34} We plan on enrolling waves of 70 participants (35 participants in each treatment condition), thus the feasibility trial allows to pilot recruitment procedures and assess feasibility of recruitment and engagement in the Facebook groups.

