Retention: With n=35 per treatment condition, the 95% confidence interval (CI) for the estimated retention rate in each condition will be within $\pm 11.8\%$ if the observed retention is 85%. Thus, given n=35 per condition, the lower limit of the 95% CI for the observed retention rate in either treatment condition should not be lower than 73.2%. App use: With n=35 per treatment condition, the lower limit of the 95% CI for observed proportion of 80% of participants meeting targets for app use in either treatment condition should not be lower than 66.7%. Acceptability: Assuming 85% retention, with n=30 available per treatment condition, the lower limit of the 95% CI for observed proportion of 80% of participants providing high acceptability ratings in either treatment condition should not be lower than 65.7%. Exploratory outcomes: We propose 6-month change in weight, 6-month change in weight loss problem solving, counselor time, and group cohesion at 6 months as exploratory because a true test of efficacy will require a fully powered trial informed by the refined procedures that will result from this feasibility study. Since the primary focus of this pilot trial is to assess feasibility to inform the design of the subsequent efficacy trial and the trial was powered to assess feasibility, not demonstrate efficacy, we only have 80% power to detect differences far larger than we expect to find in the subsequent efficacy trial. For example, taking an intent-to-treat approach, we have 80% power to detect differences of ≥ 0.68 SDs in weight change and the other exploratory outcomes. For example, if the SD=6.0%^{10,11} weight loss, we only have 80% power to detect differences in percent weight loss $\geq 4.1\%$, a difference 1.5-4 times larger than observed in previous research.

How are participants recruited?

Participants will be notified or approached about this research study through digital ads on various platforms (e.g., search engines, health websites, and social media platforms). One method we may use will be in collaboration with a company called Build Clinical. Build Clinical is a technology company that enables academic researchers to engage the exact populations needed for a given study.³⁸ Build Clinical will create the advertisements and landing page as well place the digital ads on the various platforms across the Internet. Participants will learn about the research study through these digital ads that will appear

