Adverse Events. Adverse events will be documented during the intervention and follow-up phase. AE's will be formally assessed at follow-ups by asking questions in the REDCap survey. During the intervention, AE's will be documented when a participant reports it to the weight loss counselor or posts it in the Facebook group. If it is reported during the intervention, the counselors will notify a research coordinator within 24 hours of learning of the event. UConn will then report it to the IRB (immediately if it's serious, or at the time of annual renewal). If participants gain 5% or more weight during the intervention, this will be treated as an adverse event. The participant will receive a phone call from a research coordinator, and they will be asked questions to figure out the cause of their weight gain. We will also assess Binge Eating Disorder (BED) at this time. If BED is present, we will treat it as a study-related AE. We will only assess BED once, even if there are multiple AEs for weight gain. Participants will not be removed from the intervention if they have 5% or more weight gain.

After we have completed all data analysis for the study, and it is put into a master dataset we will delete the Facebook group.

Measures

Data Collected	List of Measures	Screening/ Baseline	6-month pilot	F/up	Method
Inclusion/Exclusion criteria	Initial screening survey*	X			REDCap or Qualtrics
BMI	Height	X			REDCap
	Weight	X	X	X	REDCap
Demographics	Marital status, education, race/ethnicity, sexual orientation, work status, household income, household members*	X			REDCap
Binge Eating Disorder	SCID Eating Disorder Examination Questionnaire ⁴⁷		X**	X**	REDCap
Depression	Patient Health Questionnaire (PHQ-8 ⁴⁸)	X			REDCap
Weight Loss Problem Solving Skills	Social Problem-Solving Inventory-Revised (Modified for weight loss) ⁴⁹	X		X	REDCap
Group Climate Questionnaire	Group cohesion ⁵¹⁻⁵⁶			X	REDCap

Engagement	Facebook Engagement	X		Grytics into REDCap
App use	App use data*	X		WPI server and REDCap
Diet tracking	Data extraction*	X		MFP records
Usability Feedback	Acceptability, contamination, satisfaction, burden*, and user engagement ⁵⁰		X	REDCap and focus group

* = investigator derived

** = as needed for AEs

Psychometric properties for non-investigator derived measures:

SCID Interview for BED: The SCID's severity scales demonstrated substantial internal consistency (all Cronbach's alphas >.80), test-retest reliability, concurrent, and predictive validity.⁴⁷

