App use. In the Habit app condition, descriptive statistics will be performed to summarize the number of days participants used each feature. These numbers will be inspected relative to the use targets defined for each feature. In the MyFitnessPal condition, descriptive statistics will be performed to summarize the mean number of days participants used MyFitnessPal over the 6-month intervention. A total “app compliance” score will be developed for each participant based on the percent of days they completed of their assigned use. Exploratory analyses using ANOVAs will compare conditions on app compliance scores at 6 months.

Retention. We will calculate retention as the proportion of participants who complete the 6-month follow-up assessment in each condition and report this information using a CONSORT diagram.

Engagement. Number of Facebook reactions (e.g., like, care, wow, etc.), replies, posts, and polls per participant during the 6-month program.

Acceptability. We will report participant satisfaction.

Burden. Using descriptive statistics, we will summarize burden scores in both treatment conditions. ANOVAs will be used to compare conditions on burden.

Group Cohesion. Using ANOVAs, we will compare conditions on group cohesion and climate total and subscale scores at 6 months.

Contamination. We will report the percent of participants that used any outside programs that provided weight loss coaching/problem solving.

Weight Change (exploratory). We will calculate weight changes from baseline to 6 months in each treatment condition. We will compare percent weight change from baseline to 6 months across the two treatment conditions using a mixed effects model approach with weight as the continuous outcome variable, and time as a covariate using percent weight change calculated from all available objectively measured weekly weights. To adjust for within-subject correlation in the mixed model, first we will estimate an unstructured within-subject covariance matrix; estimates may suggest that a simpler structure, e.g., compound symmetry (random intercept) is satisfactory.

Changes in weight loss problem solving. Using a mixed effects model with weight loss problem solving as the continuous outcome variable, we will compare conditions in change in weight loss problem solving from baseline to 6 months.

Group cohesion. Using ANOVA, we will compare conditions on group cohesion measures at 6 months.

Study Removal

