Participants will be removed from the study if: 1) they do not complete all screening, baseline, and on-boarding procedures (two surveys, consent, webinar orientation, app set-up, and scale set-up, join the Facebook group), 2) become pregnant during the study period, 3) post inappropriate content in the Facebook group (e.g., bullying/harassment of others, hate speech, violent/graphic content, violating privacy of others etc.), and 4) if they choose to withdraw their participation from the study. Participants reporting that they would like to withdraw from the study will be given the option to 1) withdraw from all intervention-related activity and contacts, but still complete the final assessment or 2) withdraw from the study completely with no additional study contact. If a participant becomes pregnant during the study, they will be withdrawn from the intervention, but will be asked to complete the follow-up assessments.

Potential risks

Potential risks for being in this study includes injury while exercising, accidental exposure of personal information, and discomfort with study procedures (e.g., feeling uncomfortable

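### Apart from a call triggered by weight gain of 5% or more, adverse events are asked about systematically only in the follow-up survey, so events in people who leave the study may go unrecorded

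*Combined protocol and SAP*

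**What the plan says.** **Asking about events.** Under Adverse Events, adverse events "will be formally assessed at follow-ups by asking questions in the REDCap survey". Follow-ups places that survey in the week after the 6-month intervention ends. During the intervention, "AE's will be documented when a participant reports it to the weight loss counselor or posts it in the Facebook group". The same section has one exception: weight gain of 5% or more counts as an adverse event and leads to a coordinator's phone call, with an assessment for binge eating disorder. The Measures table has no scheduled adverse-event item; the binge eating measure is marked as needed only.

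**Leaving the study.** Under Study Removal, someone who asks to withdraw may leave the intervention and still complete the final assessment, or may "withdraw from the study completely with no additional study contact". No event question is attached to the second option.

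**Retention.** The sample-size section plans acceptability "Assuming 85% retention, with n=30 available per treatment condition". The Analytic Plan defines retention: "We will calculate retention as the proportion of participants who complete the 6-month follow-up assessment in each condition".

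**Reporting.** Data Safety Monitoring promises the safety officers a listing with duration, severity, seriousness, relatedness and action taken. It does not say whether each event was solicited or volunteered, or how many participants were never asked. The Analytic Plan has no adverse-event analysis.

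**The concern.** The plan has two ways of learning about most harms, and they differ in sensitivity. Those who answer the follow-up survey are asked directly. The others must raise the matter themselves, and a participant who has gone quiet in the Facebook group is less likely to do so. If an injury or another harm is the reason for leaving, it falls mainly on the weaker route. That dropout-related harms are the easiest to miss is an inference from the design; the documents give no figure for it.

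At stake is the completeness of the event listing. A reader of that listing could not tell whether few events among leavers means few harms or few questions. The missing-data scenarios in the Analytic Plan do not help, because they treat dropouts as responders or non-responders to the intervention and say nothing about unreported harms. The pilot is meant to inform a later efficacy trial, so the gap could carry over.

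**Working it through.** **Inputs from the documents** (How was sample size determined?)
- Enrolment: "The total number of participants that will be enrolled into the 6-month feasibility trial is 70", 35 per condition.
- Planning retention: 85%, with 30 of 35 available per condition.
- Lower limit for retention: "the lower limit of the 95% CI for the observed retention rate in either treatment condition should not be lower than 73.2" per cent.

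**Step 1. Reproduce the plan's own figure.** The Wald 95% interval has half-width 1.96 × √(p(1 − p)/n). With p = 0.85 and n = 35, this is 1.96 × √(0.85 × 0.15/35) = 0.118, so the lower limit is 85% − 11.8% = 73.2%. Both match the plan.

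**Step 2. Count those who may not complete follow-up.**
- At 85%: 35 − 30 = 5 per condition, so 10 of 70. Unrounded, 0.15 × 70 = 10.5.
- At 73.2% in both conditions: 0.268 × 70 = 18.8, about 19 of 70. The limit is stated per condition; applying it to both is a pessimistic case.

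**Step 3. Illustrate the share missed.** The documents give no adverse-event rate, so these inputs are assumptions:
- 60 completers at 10% risk, with all their events captured;
- 10 non-completers at RR times that risk, none of whom answers the survey;
- a fraction s of non-completers' events is volunteered.

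Share of participants with an event who are missed = 10 × 0.10 × RR × (1 − s) / (60 × 0.10 + 10 × 0.10 × RR).

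| RR | Participants with an event | Missed, s = 0 | Missed, s = 0.5 |
|---|---|---|---|
| 1 | 6 + 1 = 7 | 1/7 = 14% | 0.5/7 = 7% |
| 2 | 6 + 2 = 8 | 2/8 = 25% | 1/8 = 12.5% |
| 3 | 6 + 3 = 9 | 3/9 = 33% | 1.5/9 = 17% |

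The 10% cancels from the formula, so the range of 7% to 33% depends on RR, s and the number of non-completers, not on the base rate. With 19 non-completers the shares rise: at RR = 1 and s = 0, 19 × 0.10 / (51 × 0.10 + 19 × 0.10) = 1.9/7.0 = 27%.

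**The case against.** The strongest reply is that the plan is less passive than it looks.

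- **Weight gain needs no volunteering.** By default, weights pass from the Wi-Fi scale to a Fitbit account whose login staff hold (Weigh-ins). A participant who stops posting but still weighs in can be detected and called. This stands, but it covers one type of event and needs a weight reading.
- **Quiet participants can be reached.** They may message the counselor privately, and counselors may tag, message, email or call people who stop taking part (Facebook Group). This also stands. However, the outreach is optional, no event question is attached to it, and Privacy and Confidentiality says that staff do not pursue people who fail to answer contacts about app and group use.
- **The safety section makes a broader commitment.** Under AE reporting process, events during the intervention are to be assessed and followed, and a separate standard protocol is mentioned. That protocol is not among the documents and may contain an exit question. What can be said is that none is described here, and that no method or schedule of asking is given.
- **Those who leave only the intervention are covered**, provided they complete the final assessment. Participants who become pregnant are withdrawn from the intervention and asked to complete follow-up.

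A reader might infer that all non-completers are never asked. The documents do not support this. Study Design makes the follow-up assessment a survey, a focus group and a weigh-in together, so someone counted as not retained may still have answered the survey. The 85% is also a planning assumption, not a forecast.

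A reader might further infer that a safety comparison between conditions is biased. The plan specifies no adverse-event rate or between-condition comparison, only a descriptive listing. Incompleteness of that listing is as far as the text goes.

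**Conclusion.** The point holds in limited form. For events other than weight gain of 5% or more, the only systematic questioning described is in the follow-up survey, and no event question is described for complete withdrawals. About 10 of 70 participants at 85% retention, or about 19 if both conditions sat at 73.2%, may not complete follow-up and so may not be asked. The safety officers' listing may therefore be incomplete for people who leave.

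For 10 non-completers, the illustrated loss is about 7% to 33% of participants with an event. It would be tempting to quote one third as the expected shortfall. That value is the top of this range and needs triple risk in non-completers and no volunteered reports, neither of which the documents establish.

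The weakness is minor. It does not touch the feasibility outcomes and is worth correcting mainly because correction is cheap.

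**What to change.** 1. **Study Removal and Adverse Events:** when a participant says they wish to withdraw and the two options are offered, offer the follow-up survey's existing adverse-event questions as an optional form, before contact ends.
2. **Data Safety Monitoring:** list events by condition over all randomized participants, separate solicited from volunteered events, and state how many participants in each condition were not asked.

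The cost is reuse of existing REDCap questions at a contact already made, a source field in the event record, and about two minutes (an estimate) for a withdrawing participant, who may decline. The form reaches only people who announce that they are leaving; those who choose to complete the final assessment would be asked there anyway. It does not reach silent dropouts, so the count of those not asked has to be reported whether or not the form is adopted.

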Study Design: Participation starts with a simple information sheet, online eligibility survey, orientation webinar, e-consent, and then another survey to collect baseline assessment data. Eligible participants will then complete an on-boarding process, which includes app and scale set up. Participants will then be randomized and complete a 6-month intervention, and a 6-month follow-up assessment after the intervention ends (survey, focus group, and weigh-in).

Recruitment: We will post online recruitment ads that will contain a link to a simple information sheet and an online survey containing the screening questions. Ads that are done with Build Clinical will lead the participant to a landing page that will give them some more information about the study and then will have the link to bring them to the simple information sheet and survey. See recruitment section (starting on page 8) for full recruitment details.

Screening

Inclusion Criteria

- 18-65 years old
- BMI 27-45 kg/m²
- Wi-Fi connectivity at home
- Logs into Facebook at least 5 days per week over the past 2 weeks
- Has posted/replied on Facebook at least once a week in the past 2 weeks

- Able to participate in the study in English
- Interested in losing weight

Age justification: Children under 18 require different programming for weight loss and maintenance given their developmental needs. Weight loss is for elderly adults should be medically supervised, something this study is not offering.

Exclusion Criteria

- Under the age of 18 and over the age of 65
- BMI under 27 or over 45 at screening; then under 27 at the point of the first weight on scale
- Does not have Wi-Fi connectivity at home
- Does not have a Facebook account
- Does not log into Facebook at least 5 days per week over the past 2 weeks
- Did not post/reply on Facebook once a week over the past 2 weeks
- Not able to participate in the study in English
- Does not live in the United States
- Not interested in losing weight
- Pregnant/lactating or plans to become pregnant during study period
- Reports having bipolar disorder, substance abuse, psychosis, an eating disorder, or severe depression
- Had bariatric surgery or plans to have surgery during the study
- Currently taking medication affecting weight
- Has lost $\geq 5\%$ of weight in past 3 months
- Is participating or intends to participate in another weight loss program during the study that provides coaching or problem solving

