- Chronic pain that interferes with the ability to exercise

- Type 1 Diabetes
- Type 2 Diabetes
- Unable to make dietary changes or increase physical activity
- Unable to walk ¼ mile unaided without stopping
- Currently smokes or vapes nicotine
- No phone connectivity at home and work
- Has a digestive disorder/condition that precludes dietary changes
- Meets criteria for severe depression on the PHQ-8 (score of >19)
- Does not currently own a smartphone
- Smartphone type and/or version not meeting app requirements
- Participated in previous weight loss studies under the PI
- Unable to attend the orientation webinar
- If UConn employee/student, has concerns about being in a Facebook group with other UConn faculty, staff, and students
- Had major surgery in past 6 months and have not been cleared by their doctor to resume physical activity and diet changes
- Plans to have major surgery in the next 6-months
- Has an implanted cardiac defibrillator or pacemaker
- Did not complete screening and on-board processes of study (screening survey, webinar, e-consent, baseline survey, app set-up, scale set-up, etc.)
- Not willing to be audiotaped for focus groups
- Prisoner; or
- Unable to provide consent

Participants will complete screening procedures online since they may be located anywhere in the country. The screening survey will first have a description of the study and the data we will collect from them at that point (the simple information sheet). At the bottom of the information sheet, they can mark that they are interested in participating or not interested. If they mark that they are interested, it will bring them to the screening

questions to determine eligibility. The survey logic within REDCap will determine eligibility for participation based on participant responses. BuildClinical also had logic to determine eligibility. If they are ineligible, they will be notified after the survey is submitted. If they are eligible to proceed, they will be contacted by the study team via email to book a time to attend a live informational webinar.

We will not require PCP approval since we assess exclusionary medical conditions during the screening process. If conditions are reported that might put the participant at risk during the intervention, they will be excluded.

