The purpose of the webinar is to educate participants about what research is, review study procedures, how the intervention is going to work, review importance of participation of enrolled participants, and to allow participants to evaluate if joining this study is the right choice for them. This webinar is being conducted to improve study retention. Participants will receive a link to access the webinar via WebEx (under UConn's WebEx license). Once the participants are logged into the webinar, the research coordinator/assistant will proceed with the slides. Toward the end of the slides, participants will have the opportunity to use the chat function to ask questions and discuss any concerns related to the program. The webinar moderator will record in REDCap tracking which participants completed the webinar. After completion of the webinar, participants will receive an email to go over any questions they may have had during the webinar and a link to the online consent form.

As a result of the COVID-19 Pandemic, our lab is working remotely. Therefore, any phone calls or texts made to participants while our team members are working from home will be conducted via Google Voice. This is an app that gives our staff a different phone number to protect their personal information due to their inability to divert UConn phone lines to personal phones. We will not be recording any phone calls with Google Voice. Participants will be able to reach out to investigators as easily as standard calling. Participants do not need the app to contact the lab. It is important to note that some information may be retained on Google's active servers temporarily for billing UConn staff or other business purposes, and residual copies may remain in Google's backup systems. Anonymized copies of call record information, with no personally identifiable information, will be retained on Google systems to meet reporting and auditing requirements. However, this is no different than any standard phone plan.

Baseline

Participants that decide to complete the online consent process will be immediately sent the online baseline survey about demographics, depression, and weight loss problem

solving skills. Participants who do not consent will be brought to a landing page thanking them for their time learning about the study, but they will no longer be eligible to participate beyond that point.

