After the baseline survey is completed, for those that are still eligible, UConn will ship a study scale to the participant. Once the participants receive their scale, UConn staff will give the participant an option to set it up themselves or schedule a call to help them set up the scale and ensure that it is working, and we can access their data. UConn staff will then collect a baseline weight from participants to confirm their BMI for eligibility reasons.

After the BMI has been confirmed, UConn staff will do a final eligibility check, going through all previous steps done by the participant and double-check to confirm that they are eligible. If they are not, UConn staff will notify them via email. If they are eligible, UConn staff will engage in a series of emails with the participants to help them set-up the study apps and confirm they are working. If the participant prefers, the set-ups can be done over the phone as well.

Participants will need to complete both surveys (screening and baseline), webinar, consent, set-up the scale and provide the study team with a baseline weight to confirm BMI (done with scale we ship to them), and set-up all study apps before being randomized into the trial. Participants will be randomized into one of two groups.

Ineligible participants will be notified either automatically or by the research assistant/coordinator via email that they do not meet criteria for the study. Staff will use a generic response about how their pattern of responses is not a match to our eligibility criteria (the examples are provided in additional documentation). If they want to know specifics as to why they were ineligible, staff will refer the participant to email the PI so they can have a more detailed discussion about eligibility. This is being done to avoid upsetting participants and letting [name], a clinical psychologist, handle communication of more sensitive information.

Intervention

Participants will be randomized into the Habit app or calorie tracking app program. Both programs are 6-month online weight loss interventions and involve these major components: 1) monthly group meetings, and 2) counselor-led Diabetes Prevention Program (DPP) lifestyle intervention delivered via private Facebook group. The Habit condition use the Habit app and the calorie tracking condition will use a commercial app for calorie tracking.

1. Monthly Group Meetings

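### Binge eating disorder is not measured at baseline and is labelled study-related on presence alone after a 5% weight gain, so the reported count cannot separate new, worsened and pre-existing cases

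*Combined protocol and SAP*

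**What the plan says.** **Entry.** One of the Exclusion Criteria reads "Reports having bipolar disorder, substance abuse, psychosis, an eating disorder, or severe depression". It names no eating-disorder instrument or cut-off. Severe depression appears in the same line but also has a scored criterion of its own: "Meets criteria for severe depression on the PHQ-8 (score of >19".

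**Baseline.** The Baseline section describes an "online baseline survey about demographics, depression, and weight loss problem" solving survey, and no eating-disorder measure is listed. The final eligibility check consists of "going through all previous steps done by the participant and double-check to confirm that they are eligible". Apart from the BMI taken from the study scale, it adds no new assessment.

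**Measures table.** The BED row lists the "SCID Eating Disorder Examination Questionnaire", with REDCap as the method. Its Screening/Baseline cell is empty. The two later columns are marked, with a footnote limiting use to adverse events that call for it.

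**Adverse Events.** "If participants gain 5% or more weight during the intervention, this will be treated as an adverse event". A coordinator then telephones to explore why the weight was gained, and "We will also assess Binge Eating Disorder (BED) at this time". The rule that follows is "If BED is present, we will treat it as a study-related AE". BED is assessed only once per participant, even if weight-gain events recur.

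**Reporting.** Under Data Safety Monitoring, the adverse event listing for the two safety officers includes a relatedness entry for each event.

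**The concern.** Relatedness is a statement about what happened after the intervention began. Here it is fixed by a single measurement taken after the event, with no earlier value to compare it with and no stated question about onset. A participant who had BED at entry and did not report it can pass screening. If that participant later gains 5%, the case is reported in the same way as one that began during the program.

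The consequence is confined to safety reporting. The safety officers advise the investigators, the IRB and NIH on corrective action, and the pilot is meant to inform a larger efficacy trial. With 70 participants, even one BED event would be noticed, and the report would not show whether it was a new harm, a worsening, or a condition that screening did not detect.

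**Working it through.** No figure in the plan underlies this point, so there is none to reproduce. The check has two parts.

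**1. What the rule can distinguish.** Consider three participants who each gain 5% or more and have BED at the call:

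- New onset: no BED at entry. Baseline record: none. Label: study-related.
- Worsened: BED at entry, worse at the call. Baseline record: none. Label: study-related.
- Pre-existing and unchanged: BED at entry, the same at the call. Baseline record: none. Label: study-related.

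The three histories leave the same baseline record and receive the same label. The count is their sum and cannot be split from what the plan says will be collected on BED. Because assessment happens once, no later measurement helps. A participant with BED who does not gain 5% has no stated route to assessment, so the count is not a total of BED in the trial either.

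**2. How many cases this could involve.** Inputs:

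- N = 70, the total enrolment stated in the protocol.
- p = proportion with unrecognised BED at entry. Not in the documents; assumed 2% to 10%.
- g = proportion of those who gain 5% or more. Not in the documents; assumed 5% to 20%.

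Expected number with BED at entry = N × p: 70 × 0.02 = 1.4 to 70 × 0.10 = 7.

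Expected number of these labelled study-related = N × p × g. Chance of at least one = 1 − (1 − p × g)^70.

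| p | g | Expected labelled | Chance of at least one |
|---|---|---|---|
| 2% | 5% | 70 × 0.02 × 0.05 = 0.07 | 6.8% |
| 2% | 20% | 70 × 0.02 × 0.20 = 0.28 | 24.5% |
| 10% | 5% | 70 × 0.10 × 0.05 = 0.35 | 29.6% |
| 10% | 20% | 70 × 0.10 × 0.20 = 1.4 | 75.7% |

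At p = 2%, expecting one labelled case would need g = 1 / 1.4 = 71%. The calculation takes it that the assessment finds every case. It counts worsened cases together with unchanged ones, so the number whose label is actually wrong is at most the figure shown.

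**The case against.** The strongest defence is that the rule is deliberately cautious: it says BED will be treated as study-related, which errs towards over-reporting harm. A condition present at entry can also worsen during a weight-loss program, so prior presence does not by itself make the label wrong. Both points stand. They argue for keeping prompt reporting of every case, and against a simple pre-existing label that could hide worsening. They do not make the count interpretable.

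It can also be said that the adverse event listing includes duration, that the call explores the cause of the gain, and that independent safety officers with clinical psychology expertise review the reports. These could bring out onset informally, but none overrides a stated rule that depends on presence alone.

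The contrast with depression should not be pressed too far. The PHQ-8 is itself self-report; the difference is a scored instrument against a reported condition. As worded, the eating-disorder criterion is not breached by an unreported case. The screening survey items are not reproduced and may ask about eating disorders, although no BED instrument is scheduled there.

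Some stronger readings are tempting. A reader might infer that people with BED are in fact enrolled and then blamed on the program; the documents show only that this can happen. A reader might take 1.4 to 7 of 70 as the number mislabelled; that is an assumed number at entry, and only those who gain 5% or more are ever assessed. A reader might conclude that a trial aim fails; the aims are feasibility outcomes, and no analysis in the Analytic Plan uses BED.

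**Conclusion.** The point holds in a limited form. The eating-disorder exclusion rests on what the person reports, BED has no baseline measurement, and BED found after a gain of 5% or more is called study-related whatever its onset. Among those participants the BED count mixes new-onset, worsened and unchanged cases and cannot be read as harm caused by the program. For a pre-existing case that has not changed, the label is wrong.

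The expected size is small: about 0.07 to 1.4 pre-existing cases labelled among 70, with a 7% to 76% chance of at least one. Both rates behind this range are assumptions. The feasibility outcomes are unaffected. The change is worth making because it is cheap and because the safety record of a pilot is carried forward to the next trial.

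**What to change.** 1. **At the call already planned,** record when BED began relative to randomization and whether it has worsened since. Report each BED event as new-onset, worsened, or pre-existing and unchanged. Prompt reporting of every case can stay as a cautious default, but the relatedness entry should follow this classification and not presence alone. Cost: a few questions and a sentence or two in the Adverse Events section. Limit: onset is recalled by someone who did not report the disorder at screening, which is why the second step adds value.

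2. **Add the listed BED measure to the baseline survey,** completed before the scale is shipped, and state how its result supports the existing eating-disorder exclusion, as the PHQ-8 does for severe depression. This also gives a baseline status for later comparison. Cost: time added to a survey now put at 20 minutes, and perhaps a few more screen failures.

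3. **Reconcile the name of the instrument.** The Measures table calls it a questionnaire collected in REDCap; the psychometric notes below the table call it a SCID interview. If it is an interview, the second step needs staff time for every consented participant, and only the onset and worsening items are cheap.
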